The determination of the specific composition of the 3 types of EO made it possible to quantify the exact concentration of the different components of each of the EO, choosing the EO with the highest concentration of components with antimicrobial activity and the lowest concentration of components susceptible to interaction with other drugs or to produce allergies in the participant, such as terpinolene, alpha-terpinene and sabinene and the aged components of EO(7-10). Specifically, the main component in the 3 EO samples was terpinen-4-ol, with a concentration between 28.47% and 29.15%, followed by gamma-terpinene and alpha-terpinene (Table 2). These three components accounted for approximately 65% of the total EO in the 3 samples analyzed. On the other hand, alpha-terpineol and eucalyptol were found to be the fourth and fifth most concentrated components, with percentages between 3.85%-5.85% and 4.12%-5.81%, respectively. These two, along with m-cymene, alpha-pinene, and terpinolene, made up about 24% of the total EO. The rest of the EO was made up of up to 22 different compounds with minority percentages, considered together as traces. For all the above results, the EO of *M. alternifolia* of the brand Esencias Lozano® was used, since it was the EO that presented the highest percentage of the components of terpinen-4-ol, eucalyptol and alpha-terpineol, whose antimicrobial activity has been described in the bibliography(7,11-14).

Table 2. Percentages of the different components according to the EO studied in the CG-MS.

Components	Trademarks of EO		
	Naissance®	Marnys®	Esencias Lozano®
Terpinen-4-ol	28.47%	29.10%	29.15%
Gamma-terpinene	21.92%	20.42%	22.86%
Alpha-Terpinene	13.10%	11.23%	13.58%
Alpha-terpineol	3.85%	4.03%	5.85%
Eucalyptol	4.12%	4.82%	5.81%
M-cymene	3.40%	5.28%	4.96%
Alpha-pinene	3.18%	3.15%	5.12%
Terpinolene	4.65%	4.26%	3.72%
Traces	17.31%	17.71%	8.95%
Total	100%	100%	100%

®: trademark; %: percentage of the component in the sample.

Test results for microbiological diagnostics

After reading the tests performed for microbiological diagnosis, it was determined that, of the 49 total participants, 32 (65.3%) were positive for skin infections. Of these 32 participants, 4 (12.5%) had fungal infection, 19 (59.4%) showed bacterial infection, and 9 (28.1%) had mixed fungal and bacterial infections simultaneously.

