	East.	Err. East	IC 95%		East.	Err. East	IC 95%	
			Lim. Inf.	Lim. Sup.			Lim. Inf.	Lim. Sup.
Treatment 1%	11.61	2.68	6.36	16.86	-	-	-	-
Treatment 0.5%	14.00	4.04	6.09	21.91	-	-	-	-

Est: statistical survival test; Err. Est: statistician error; CI, confidence interval; Lim. Inf: lower bound; Lim. Sup: upper limit; "-": data not available.

Similarly, to evaluate whether the EO-enriched cream was effective against bacterial infections, the cumulative survival curves for both treatments were plotted (Figure 5). In this case, the treatment curve at 0.5% concentration showed better results than the 1% treatment curve.

[figure not shown]

Figure 5. Cumulative survival curves as a function of the two treatments for bacterial infections.

Thus, the mean time to achieve remission in the T1 group (1%) was 49.35 days, compared to 44.82 days in the T2 group (0.5%) (Table 5). This indicated that the treatment of the T2 group was better, since the infection remitted 5 days earlier on average, although when comparing both treatments using the Long-rank test, no statistically significant differences were found (p -value=0.130). Median survival was 60.00 days for treatment at 0.5%, so half of the participants in the T2 group achieved remission at the end of the study. This value could not be computed for the 1% treatment, indicating that less than half of the subjects in this group experienced resolution of the infection at the end of the trial (Table 5).

Table 5. Mean and mediansurvival time (in days) of remission of bacterial infection for the two EC concentrations.

Group	Media				Median			
	East.	Err. east.	IC 95%		East.	Err. east.	IC 95%	
			Lim. Inf.	Lim. Sup.			Lim. Inf.	Lim. Sup.
Treatment 1%	49.35	2.38	44.68	54.01	-	-	-	-
Treatment 0.5%	44.82	4.38	36.2	53.40	60.0	6.37	47.51	72.49

Est: statistical survival test; Err. Est: statistician error; CI, confidence interval; Lim. Inf: lower bound; Lim. Sup: upper limit; "-": data not available.

Relationship between infections and the rest of the variables analyzed

In relation to hygiene habits, it was found that most of the participants washed their feet daily, used flip-flops in swimming pools or showers, wore breathable footwear and cotton socks, and changed their socks daily (Table 6), although it is true that these habits did not show a statistically significant relationship with respect to the presence or absence of skin infections ($p\text{-value} \geq 0.103$) (Table 7).

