Variable	B (coef.)	Exp(B)	IC 95%		p-value
			Lim. Inf.	Lim. Sup	
Stature	-0.02	0.98	0.73	1.30	0.874
Weight	0.01	1.01	0.73	1.40	0.948
BMI	-0.04	0.96	0.39	2.40	0.938
Age	0.03	1.03	0.54	1.97	0.918
Sex	-0.64	0.52	0.20	1.35	0.181

Coef: coefficient; Exp: exponent; B: correlation coefficient; CI, confidence interval; Lim. Inf: lower bound; Lim. Sup: upper limit; *: statistically significant.

[figure not shown]
Regarding the possible relationship between anthropometric and sociodemographic variables and the efficacy of treatment for bacterial infections, it was observed that only sex showed a statistically significant relationship (p-value=0.028) (Table 9).

Table 9. Cox model for different anthropometric and sociodemographic variables and bacterial infection.

Variable	B (coef.)	Exp(B)	IC 95%		p-value
			Lim. Inf.	Lim. Sup	
Stature	0.11	1.12	0.82	1.54	0.484
Weight	-0.08	0.93	0.64	1.34	0.684
BMI	0.13	1.14	0.41	3.21	0.803
Age	0.55	1.74	0.82	3.67	0.146
Sex	1.41*	4.11	1.16	14.50	0.028*

Coef: coefficient; Exp: exponent; B: correlation coefficient; CI, confidence interval; Lim. Inf: lower bound; Lim. Sup: upper limit; *: statistically significant.

To assess the efficacy of the treatment over time according to sex, a cumulative survival curve was used (Figure 6) and the proportion of individuals in whom the resolution of the infection over time was observed was represented, observing that the healing time was shorter in women than in men and, therefore, a faster resolution of bacterial infection is observed in women.

**Figure 6.** Cumulative survival curve as a function of sex.

Finally, in relation to skin hydration, significant differences were obtained according to sex (p-value ≤ 0.010), with women having higher hydration averages (Table 10).

Table 10. Results of the Kruskal-Wallis tests for the analysis of hydration according to sex.

Landmarks per foot	Sex	Initial		15 days		30 days		45 days		60 days	
		Media±Sd	p-value								
Dorsal R	Woman	34.507±9.834	0.146	41.904±13.322	0.511	44.364±13.907	0.439	42.674±13.989	0.408	43.871±16.218	0.171
	Man	29.306±9.159		40.966±18.823		44.358±21.589		37.933±10.723		36.837±12.851	
Digital Plant R	Woman	29.453±11.772	0.115	39.738±16.234	0.075	37.465±14.911	0.044*	36.737±15.137	0.048*	45.303±18.070	0.015*
	Man	23.450±10.769		31.391±12.869		27.967±16.632		28.604±10.934		24.685±11.913	
Inner Arc R	Woman	28.401±19.944	0.221	32.539±22.396	0.541	31.884±20.830	0.318	29.654±18.746	0.318	30.272±18.633	0.480

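### The claim that bacterial infection clears faster in women rests on the smallest of ten uncorrected Cox p-values, from model outputs that are hard to reconcile with the documented cases

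*Combined protocol and SAP*

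**What the plan says.** Section 1, Variables and statistical analysis, names Cox regression for the influence of different variables on remission and tests everything at 0.05. Bonferroni is stated only for the pairwise hydration comparisons. The section does not give the analysis set, the coding of sex, the handling of ties, or whether covariates were entered jointly or one at a time.

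Tables 8 (fungal) and 9 (bacterial) each list stature, weight, BMI, age and sex. Neither lists treatment arm. For bacterial infections the text says that "it was observed that only sex showed a statistically significant relationship (p-value=0.028) (Table 9"). The sex row of Table 9 reads "Sex 1.41* 4.11 1.16 14.50 0.028", and the text before Figure 6 concludes that "a faster resolution of bacterial infection is observed in women".

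The number of remissions is never printed. Under Efficacy of treatments, the text for Table 5 says of T1 that "less than half of the subjects in this group experienced resolution of the infection at the end of the trial" and of T2 that "half of the participants in the T2 group achieved remission at the end of the study". Baseline case numbers come from the microbiological results, where "19 (59.4%) showed bacterial infection, and 9 (28.1%) had mixed fungal and bacterial infections simultaneously", and from Table 3, which splits them by sex.

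**The concern.** This is the only predictor of remission reported as significant, and it is stated as a finding without qualification. Two things count against it. It was picked out of ten tests with no allowance for the number examined. Its confidence interval also looks tight for so few remissions, once the case counts elsewhere in the same document are set beside it. If the rows or events behind Table 9 are not the documented infected participants, neither the interval nor the p-value can be relied on.

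**Working it through.** 1. **Table 9 agrees with itself.** SE = ln(14.50/1.16)/3.92 = 0.644. z = ln(4.11)/0.644 = 2.19, two-sided p = 0.028, as printed.

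2. **Multiplicity.** There are ten Cox p-values. After 0.028, the next smallest in Table 9 is "Age 0.55 1.74 0.82 3.67 0.146", and the smallest in Table 8 is "Sex -0.64 0.52 0.20 1.35 0.181". Bonferroni: 5 × 0.028 = 0.14, and 10 × 0.028 = 0.28. Ten independent null tests give at least one p < 0.05 with probability 1 − 0.95^10 = 0.40.

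3. **Remissions implied by the text.** Bacterial cases number 19 + 9 = 28: women 13 + 7 = 20, men 6 + 2 = 8. Infected participants are 23 in T1 and 9 in T2, and 4 of these 32 have fungal infection only. So T1 has 19 to 23 bacterial cases and T2 has 9 to 5. Fewer than half of T1 plus about half of T2 gives about 14 (for example 11 of 23 plus 3 of 5). If every T2 case remitted, the maximum is 9 + 9 = 18. This assumes one row per infected participant.

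4. **Sex-only Cox fit, 20 women and 8 men (Breslow ties).** I enumerated the possible remission patterns.
   - Events on the culture days only (30 and 60): with HR between 3.6 and 4.7, the smallest SE is 1.04 at up to 14 remissions and 0.75 at up to 18. An SE near 0.644 first appears at 20.
   - Events at any 15-day visit: with 18 remissions, the largest HR that has SE of 0.65 or less is 3.61. HR near 4.11 with SE near 0.644 first appears at 19.

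5. **Joint five-covariate fit.** At the fitted values, the sex SE cannot be below √(1/d_women + 1/d_men), where d is the number of remissions, whatever else is in the model. With 14 remissions, 11 women and 3 men give 0.651, which is too large; 10 and 4 give 0.592. So an SE of 0.644 needs at least 4 of 8 men and at most 10 of 20 women remitted, beside an HR of 4 in favour of women. Among 396 random simulated fits with 18 or fewer events and HR 3.5 to 4.8 (covariates assumed, built to resemble Table 1), none had SE of 0.65 or less; the smallest was 0.716. A deliberate search did reach HR 4.05 with SE 0.653 at 14 events, and a full match at 18.

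6. **Table 8.** The sex SE is ln(1.35/0.20)/3.92 = 0.487. Fungal cases number 4 + 9 = 13: women 3 + 7 = 10, men 1 + 2 = 3. Even if all remitted, the bound in step 5 is √(1/10 + 1/3) = 0.658. The printed value cannot come from those 13 cases. At the most favourable split, SE² ≥ 4/d requires d ≥ 4/0.487² = 16.9, that is 17 events.

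7. **Survival means.** With remission dated at 15-day visits and nobody censored before day 60, a mean over n rows is 15k/n for a whole number k. For n below 50, the T1 means of 11.61 (360/31) and 49.35 (1530/31) each fit only n = 31. T1 had 25 participants. The bacterial mean and its SE of 2.38 together match 8 remissions at day 30, 6 at day 45 and 17 censored: 14 of 31, SE 2.376. T2's fungal mean of 14.00 fits n = 15, 30 or 45, against 12 participants. T2's bacterial mean of 44.82 fits no n below 50. If T2 had 15 rows and about half remitted, the total would be about 14 + 7 or 8 = 21 to 22.

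8. **Case counts.** Table 6 has 20 bacterial infections, against 28 in step 3.

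9. **Events per coefficient.** 14/5 = 2.8 to 22/5 = 4.4.

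**The case against.** The strongest reply is that no remission count is printed, so any ceiling of 14 or 18 is the reader's construction and assumes one row per infected participant. Step 7 suggests the survival analyses used other rows. With 21 to 22 remissions, even a sex-only fit could give the printed SE if it otherwise behaved like the 20:8 case. The usual null-information formula needs only (1/0.644²)/(20 × 8/28²) = 2.41/0.204 = 11.8 events, and the search in step 5 shows that a joint model is not ruled out. On multiplicity, the size of the family is a choice, and Bonferroni is conservative when stature, weight and BMI are correlated. Finally, sex is a secondary covariate, and no conclusion on efficacy or concentration depends on it.

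Much of this stands. A reader might infer that Table 9's interval is simply too narrow, or that participants still positive at day 60 were counted as remitted. The documents support neither as a flat statement. A reader might also take Table 8's HR of 0.52 as showing the opposite sex effect; with an interval that includes 1, a different infection and unstated coding, it does not.

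The reply does not rescue the conclusion. The null-information formula assumes no sex effect and does not describe precision at an HR of 4. If the rows are not the documented participants, the analysis set is unexplained. No family containing the five Table 9 covariates brings the Bonferroni p-value below 0.14.

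**Conclusion.** The unqualified statement that women clear bacterial infection faster should not stand. After correction, p = 0.028 becomes 0.14 (five tests) or 0.28 (ten), with an inferred 2.8 to 4.4 remissions per coefficient and no arm term listed.

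The printed precision is hard to reconcile with the 28 documented cases. A sex-only fit needs about 19 to 20 remissions, against about 14 and at most 18 implied if each infected participant is one row. For a joint model it is unlikely but possible. The firmest discrepancies are Table 8's sex SE (0.487 against a minimum of 0.658), T1 survival means that fit only 31 rows for 25 participants (assuming the visit grid and complete follow-up), and 28 against 20 bacterial infections. Whether the analysis set, the row structure or the event coding is responsible cannot be determined from the documents.

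**What to change.** - Reconcile the analysis set, row structure and event/censoring coding behind Tables 4, 5, 8 and 9, and the bacterial case count in Table 6 with that in Table 3.
- Re-run the Cox model on one row per documented infected participant, censoring those still positive at day 60, with sex and arm only, for example with a Firth penalty. State the coding of sex and the handling of ties.
- Print remitted/total by sex and arm, and multiplicity-adjusted p-values with the family of tests named.
- Delete the sentence on faster resolution in women, or label it exploratory.

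The cost is a re-run on existing data and edits to the affected tables, Figure 6 and one sentence. The downside is that the sex result will probably lose significance.

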Statistical analysis was performed using the statistical analysis program IBM-SPSS Statistics for Windows version 25 (IBM Corp. Armonk, NY, USA). Some figures have been obtained using the Python programming language, using the Seaborn library (Waskom, M. L., (2021). Seaborn: statistical data visualization. *Journal of Open-Source Software*, 6(60), 3021, <https://doi.org/10.21105/joss.03021>).

Normality was assessed using the Shapiro-Wilk test. To evaluate the influence of different variables on infection remission, a Cox regression model was used, and survival curves of significant factors were plotted. To compare the efficacy of different EC concentrations, survival curves were compared using the Log-rank test. The Mann-Whitney U test was used to assess hydration averages according to sex. To check if there were improvements in hydration due to the use of the cream with different concentrations of EC (T1 and T2) compared to the control group (T0), hydration levels were compared using Kruskal-Wallis tests, using the Mann-Whitney U test with correction of p-values by the Bonferroni method for multiple comparisons.

In all statistical tests, significance was considered when p-value<0.05 and high significance when p-value<0.01.

2. Results

Analysis of the Elemental Composition of Commercial S. S.

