Table 6. Contingency table between hygiene habits and skin infections.

Category	Fungal infection		Total	Bacterial infection		Total
	No	Yes		No	Yes	
Frequency of foot washing						
1 time every 2 days	2 (4.88%)	-	2 (4.08%)	2 (6.90%)	-	2 (4.08%)
Daily	33 (80.49%)	8 (100.00%)	41 (83.67%)	23 (79.31%)	18 (90.00%)	41 (83.67%)
2 times a day	6 (14.63%)	-	6 (12.24%)	4 (13.79%)	2 (10.00%)	6 (12.24%)
Total	41 (83.67%)	8 (16.33%)	49	29 (59.18%)	20 (40.82%)	49
Flip flops in the shower						
No	7 (17.07%)	2 (25.00%)	9 (18.37%)	8 (27.59%)	1 (5.00%)	9 (18.37%)
Yes	34 (82.93%)	6 (75.00%)	40 (81.63%)	21 (72.41%)	19 (95.00%)	40 (81.63%)
Total	41 (83.67%)	8 (16.33%)	49	29 (59.18%)	20 (40.82%)	49
Type of footwear						
Non-breathable	18 (43.90%)	4 (50.00%)	22 (44.90%)	12 (41.38%)	10 (50.00%)	22 (44.90%)
Breathable	23 (56.10%)	4 (50.00%)	27 (55.10%)	17 (58.62%)	10 (50.00%)	27 (55.10%)
Total	41 (83.67%)	8 (16.33%)	49	29 (59.18%)	20 (40.82%)	49
Sock Type						
Cotton	21 (51.22%)	6 (75.00%)	27 (55.10%)	17 (58.62%)	10 (50.00%)	27 (55.10%)
Polyester	10 (24.39%)	-	10 (20.41%)	6 (20.69%)	4 (20.00%)	10 (20.41%)
I don't know	10 (24.39%)	2 (25.00%)	12 (24.49%)	6 (20.69%)	6 (30.00%)	12 (24.49%)
Total	41 (83.67%)	8 (16.33%)	49	29 (59.18%)	20 (40.82%)	49
Daily sock change						
1 time every 2 days	5 (12.20%)	-	5 (10.20%)	1 (3.45%)	4 (20.00%)	5 (10.20%)
Daily	32 (78.05%)	8 (100.00%)	40 (81.63%)	26 (89.66%)	14 (70.00%)	40 (81.63%)
2 times a day	4 (9.76%)	-	4 (8.16%)	2 (6.90%)	2 (10.00%)	4 (8.16%)
Total	41 (83.67%)	8 (16.33%)	49	29 (59.18%)	20 (40.82%)	49

"-": data not available, %: percentage.

Table 7. Relationship between hygiene habits and skin infections.

Variables	Fungal infection		Bacterial infection	
	χ^2	p-value	χ^2	p-value
Frequency of foot washing	1.87	0.393	1.68	0.432
Flip flops in the shower	0.00	0.976	2.66	0.103
Type of footwear	0.00	1.000	0.09	0.761
Sock Type	2.64	0.267	0.58	0.748
Daily sock change	2.15	0.542	4.08	0.252

χ^2 : Chi-Square

On the other hand, the possible relationship between anthropometric and sociodemographic variables and treatment efficacy for fungal infections was examined, where no statistically significant association was observed ($p\text{-values} \geq 0.145$) (Table 8). Therefore, for this sample, anthropometric and sociodemographic variables did not seem to be critical factors in the efficacy of treatment for fungal infections of the foot.

Table 8. Cox model for different anthropometric and sociodemographic variables and fungal infection.

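### The Cox results and the curve by sex show associations with time to remission in participants on oil-enriched cream; they say nothing about treatment efficacy by sex or by any other covariate

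*Combined protocol and SAP*

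**What the plan says.** The section *Variables and statistical analysis* gives the aim as an association with remission: "To evaluate the influence of different variables on infection remission, a Cox regression model was used".

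The Results, under *Relationship between infections and the rest of the variables analyzed*, report that model as being about efficacy.

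- The conclusion before Table 8 is that "anthropometric and sociodemographic variables did not seem to be critical factors in the efficacy of treatment for fungal infections of the foot".
- The sentence before Table 9 concerns "the efficacy of treatment for bacterial infections, it was observed that only sex showed a statistically significant relationship".
- Figure 6 is introduced with "To assess the efficacy of the treatment over time according to sex, a cumulative survival curve was used". The same paragraph closes on a narrower statement: "the healing time was shorter in women than in men and, therefore, a faster resolution of bacterial infection is observed in women".

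Table 9 is captioned "Cox model for different anthropometric and sociodemographic variables and bacterial infection". Its rows, like those of Table 8, are stature, weight, BMI, age and sex. No row for cream or concentration appears, and there is no product term. Under *Randomization, masking, and experimental design*, the control group (T0, base cream without oil, n=12) has no infected participant. The 32 infected participants are all on oil-enriched cream, 23 in T1 (1%) and 9 in T2 (0.5%).

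**The concern.** Whether a variable relates to efficacy is a question about treatment effect: does the benefit of the oil over no oil differ between women and men? The reported analysis asks something else, namely whether women and men on the oil-enriched creams remit at different rates. Either answer can be true without the other. Women might clear bacteria faster on any cream. Conversely, a variable might change the effect of the oil yet show no overall association with remission.

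Neither log-rank comparison of the two concentrations was significant (fungal p=0.611, bacterial p=0.130), so sex is the only significant remission result in the document. A reader who takes the efficacy wording at face value could conclude that the cream works better in women. A reader of the fungal paragraph could conclude that age, sex and body size have been shown not to matter to its effect. These analyses can support neither conclusion, whatever the p-value.

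**Working it through.** **1. The plan's own figure.** From the sex row of Table 9 (4.11; 1.16 to 14.50):

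- SE = ln(14.50/1.16)/(2 × 1.96) = 2.526/3.92 = 0.644
- z = ln(4.11)/0.644 = 1.413/0.644 = 2.19
- two-sided p = 0.0283, against 0.028 printed

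The arithmetic is sound. The question is what the coefficient estimates.

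**2. What the coefficient contains.** Write λ for the remission rate, W and M for women and men, and oil and base for the creams. Then

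λ(W,oil)/λ(M,oil) = [λ(W,base)/λ(M,base)] × [oil effect in W / oil effect in M].

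Table 9 estimates the left side, 4.11. The first factor on the right is the prognostic ratio; the second is the difference in efficacy. With no infected participant in T0, the data say nothing about the first factor, so the second cannot be recovered. For assumed prognostic ratios:

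| Assumed prognostic ratio | Implied ratio of oil effects, W to M |
|---|---|
| 1 | 4.11/1 = 4.11 |
| 2 | 4.11/2 = 2.06 |
| 4.11 | 4.11/4.11 = 1.00 |
| 8 | 4.11/8 = 0.51 |

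The same hazard ratio fits an oil effect larger, equal or smaller in women.

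**3. The fungal results.** The argument in step 2 applies to every row of Table 8. The intervals are also wide even for an association with remission: 0.20 to 1.35 for sex, 0.54 to 1.97 for age, 0.39 to 2.40 for BMI. Absence of significance here excludes little.

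**4. The analysis set.** It is not stated for Tables 8 and 9. For the Table 8 sex row, SE = ln(1.35/0.20)/3.92 = 1.910/3.92 = 0.487. For a two-level covariate coded one unit apart, each event contributes at most 1/4 to the Cox information, so events ≥ 4/SE² = 4/0.237 = 16.9, that is, at least 17. Table 3 has 4 fungal + 9 mixed = 13 participants, and Table 6 counts 8 fungal. So the model was not fitted to the Table 3 cases with one event per participant. In addition, the text gives 0.145 as the lower limit of the Table 8 p-values, but the smallest one printed there is 0.181.

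**5. What an interaction could add.** Only sex by concentration can be fitted. Assume 20 women and 8 men with bacterial or mixed infection (Table 3: 13 + 7 and 6 + 2) and the 23:9 split of all infected participants.

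- Events implied by Table 9: 1/(0.644² × 20/28 × 8/28) = 11.8, about 12
- SE of the interaction: 1/√(12 × 0.204 × 0.202) = 1.42
- A 95% interval would extend a factor of exp(1.96 × 1.42) ≈ 16 either side of the estimate
- Power for a ratio of hazard ratios of 4.11 is about 17%; 80% power needs a ratio of about 54
- Over 8 to 28 events, power runs from 13% to 33% and the ratio needed from 131 to 14

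**The case against.** The strongest reply is that this is loose wording and not a wrong analysis. The methods section states the aim correctly, and the planned model is the one that was run. Elsewhere the authors use efficacy as shorthand for time to remission. The fungal sentence is hedged, and the captions of Tables 8 and 9 and Figure 6 do not mention efficacy. The underlying limitation is that T0 has no infected participants, which affects any comparison with oil-free cream, not only the one by sex.

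Most of that stands, and it limits the point to a few sentences. It does not remove it. The fungal paragraph draws an explicit inference about efficacy from non-significant main effects, and the text before Table 9 and Figure 6 sets a question that the analysis cannot answer.

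Three stronger readings are tempting, and the documents do not support them.

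- *The sex difference is purely prognostic.* Nothing shows this. Step 2 of the working cuts both ways: the two explanations cannot be separated.
- *The authors declare that the cream works better in women.* No sentence says so. The closing statement on Figure 6 claims only faster resolution in women, which is a fair description of the association.
- *The sex test has an inflated false-positive rate.* A simulation with no treatment effect, a sex hazard ratio of 4.11, 20 women, 8 men and remission read at days 30 and 60 gives a significant log-rank test by sex in 19%, 36%, 47% and 65% of trials, for assumed day-60 remission in men of 10%, 15%, 20% and 30%. That is power to detect a sex effect that was put in; with no sex effect the rate is 3% to 5%. The last case also implies 17.8/28 = 64% remission overall, although the Results report less than half in T1 and half in T2. The simulation shows only that a sex effect can be significant with no efficacy at all.

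**Conclusion.** The point holds as one of interpretation. Tables 8 and 9 and Figure 6 describe associations with time to remission. The sex finding for bacterial infection is one such association, imprecise (interval 1.16 to 14.50) and resting on roughly 12 events if the Table 3 counts apply. It supports no inference on efficacy by sex, and the fungal results do not show that the listed variables are unimportant to efficacy.

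This conclusion rests on two documented facts: the tables report no treatment term, and no infected participant received the oil-free cream. It does not depend on any simulation or on the unstated analysis set. The event count and the interaction figures do depend on the Table 3 counts and the 23:9 split, which are assumptions. The mismatch between Tables 8 and 3 shows that those counts cannot be taken for granted.

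**What to change.** 1. In the text before Table 8, the text before Table 9 and the sentence introducing Figure 6, replace the references to treatment efficacy with *time to remission among infected participants receiving the oil-enriched cream*. This matches the aim in the methods section. No caption needs changing.
2. Describe sex as an exploratory factor associated with remission of bacterial infection, and say that no inference on efficacy by sex is made.
3. Delete the statement that these variables are not critical to efficacy for fungal infection.
4. For Tables 8 and 9, state the analysis set, the counting unit, the number of events and the coding of sex, and reconcile Table 8 with the Table 3 counts.
5. Optionally, report a sex-by-concentration interaction with its 95% CI as exploratory, saying that it addresses only 1% versus 0.5% and is very imprecise.

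Items 1 to 3 are edits to a few sentences. Item 4 needs a look at the existing analysis files, and item 5 one further model on existing data. The downside is a more modest claim about sex.
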